8.2 Measures taken to minimize or avoid bias

The clinical investigation is designed and will be conducted, analyzed, and reported based on an internal Standard Operating Procedure (SOP) system to minimize and avoid any bias.

A maximum number of patients per investigational site is defined in order to avoid a center effect (see section 11.13).

8.3 Endpoints and hypotheses

8.3.1 Primary endpoints and hypotheses

The global primary hypothesis consists of two primary hypotheses related to the SADE-free rate in group A and SADE-free rate related in group B, respectively. The global primary alternative hypothesis is accepted when the primary alternative hypothesis for group A or the primary alternative hypothesis related to group B, or both can be accepted.

8.3.1.1 **Group A:** Ilivia family related SADE-free rate through 3 months

The safety of the Ilivia ICD family will be evaluated by asking the investigator to record any adverse event. While all adverse events have to be recorded throughout the study, only the Serious Adverse Device Effects (SADE) possibly or securely related to the Ilivia ICD family devices (SADE-d_{Ilivia}) until 3-month follow-up are counted for this primary endpoint. Securely procedure related Serious Adverse Device Effects (SADE-p_{Ilivia}) are not counted. Further definitions are given in section 18.11. The primary hypothesis evaluates the SADE-d_{Ilivia} free rate (Ilivia_{SADE_free}). It is expected, that the rate will be significantly above 90%, the corresponding hypotheses definitions are:

Null hypothesis: $H_{0_Ilivia} : Ilivia_{SADE_free} \leq 90\%$

Alternative hypothesis: $H_{A_Ilivia} : Ilivia_{SADE_free} > 90\%$

The parameter of interest "Ilivia_{SADE_free}" is the device related SADE-d free rate per patient, which will be calculated by

$$Ilivia_{SADE_free} = [1 - \text{number of patients with one or more ICD related SADEs (SADE-d}_{Ilivia}\text{) until 3-month follow-up divided by all patients in the analysis set}] * 100\%.$$

SADEs will be adjudicated by an internal adjudication board, whereby the seriousness and device relatedness will be re-examined. If any amply documented external physical influence (e.g. accident, sport, twiddling) or medical AE caused the SADE, it does not contribute to this endpoint. SADEs that occur later than the 3-months follow-up do not contribute to this endpoint.

8.3.1.2 **Group B:** Plexa related SADE-free rate through 3 months

The safety of the Plexa right ventricular lead will be evaluated by asking the investigator to record any adverse event. While all adverse events have to be recorded throughout the study, only the Serious Adverse Device Effects (SADE) possibly or securely related to the Plexa ICD lead (SADE-d_{Plexa}) until 3-month follow-up and meeting predefined criteria (see 18.11) are counted for this primary endpoint. Securely procedure related Serious Adverse Device Effects (SADE-p_{Plexa}) are not counted. The primary hypothesis evaluates the SADE-d_{Plexa} free rate (Plexa_{SADE_free}). It is expected, that the rate will be significantly above 90%, the corresponding hypotheses definitions are:

Null hypothesis: $H_{0_Plexa} : Plexa_{SADE_free} \leq 90\%$

Alternative hypothesis: $H_{A_Plexa} : Plexa_{SADE_free} > 90\%$

The parameter of interest "Plexa_{SADE_free}" is the SADE-free rate per patient, which will be calculated by

$$Plexa_{SADE_free} = [1 - \text{number of patients with one or more Plexa-related SADEs (SADE-d}_{Plexa}\text{) until 3-month follow-up divided by all patients in the analysis set}] * 100\%.$$

SADEs will be adjudicated by an internal adjudication board, whereby the seriousness and device relatedness will be re-examined. If any amply documented external physical influence (e.g. accident, sport, twiddling) or medical AE caused the SADE, it does not contribute to this endpoint. SADEs that occur later than the 3-months follow-up do not contribute to this endpoint.

8.3.2 Secondary endpoints and hypotheses

The following secondary endpoints have been defined for the two groups:

8.3.2.1 Secondary endpoints **Group A:** Ilivia family

8.3.2.1.1 Percentage of patients with successful fast ventricular arrhythmia conversion by ATP one-shot at 6-month follow-up

This endpoint examines the percentage of patients with successful conversion of ventricular arrhythmia detected in the VF zone by ATP one-shot of all patients with such episodes.

Events will only be included in the analysis of this endpoint if

- 1) the arrhythmia was detected in the VF detection zone, and
- 2) if it was classified as true ventricular tachyarrhythmia by the investigator, and
- 3) if ATP one-shot was delivered with the recommended programming (8 pulses with 88% R-S1).

The period under observation starts with the implantation and lasts until the 6-month follow-up. The parameter of interest Conversion_{R-S1_88%} is defined as following:

Conversion_{R-S1_88%} = (Number of patients with at least one successful conversion / Number of patients with events as defined here) * 100%.

Thereby, a patient is considered to have experienced successful conversion if at least one episode detected in the VF zone in that patient was converted by ATP one-shot therapies at the recommended programming, i.e ATP one-shot was beneficial and shock delivery could be avoided.

No hypotheses are pre-specified for this endpoint due to the low expected number of episodes.

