4.7.5 Early ATP one-shot

The new function Early ATP one-shot enables a delivery of ATP prior to fulfilment of the programmed detection counter in the VF zone if a stability criterion is fulfilled and if a VF detection counter of at least 16 of 20 is programmed. If the early delivery of ATP one shot is activated, it uses a separate counter (12 out of 16). If this separate counter is fulfilled and if the stability is given, the early ATP one shot is delivered. For the time of ATP delivery, the VF counter is frozen and it continues to count after the ATP delivery for the initial detection. If the early delivery of ATP one shot is successful, the VF counter will not be fulfilled and no shock therapy will be delivered.

With the help of this feature the potential drawback of the prolonged VF detection counter shall be mitigated that initially stable fast VTs might deteriorate into irregular VF that cannot be treated successfully with ATP.

With the help of this feature, the activation rate and success rate of the ATP one shot feature is expected to be improved resulting in a potential decrease of shock therapy especially in devices with very long VF counters. In patients whose devices are programmed with VF counters lower than 16 out of 20, early ATP one-shot cannot be programmed.

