8.5.5 ATP one-shot programming

Prior to discharge ATP one-shot has to be programmed for patients participating in **group A** of the study. ATP one-shot has to be programmed with 8 pulses and a cycle length of 88% of the ventricular tachyarrhythmia cycle length for all patients eligible for the programming. If patients are programmed to other parameters a reason for deviation from the programming has to be provided. Furthermore, programming of Early ATP one-shot is recommended and will be documented.

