data_SAR	Yes	Ilivia_secEP_analysis_set_SAR ⁷⁵	Analysis set Ilivia secondary endpoint	nominal	Yes /No
data_SAR	Yes	Ilivia_secEP_SAR ⁷⁶	Any successful ATP (secondary endpoint Ilivia)	nominal	Yes /No

Beyond the number of patients with endpoint relevant episodes, also the number of episodes, in which ATP-one-shot was delivered (as defined "relevant" in the footnote below) and thereof the number of episodes in which ATP-one-shot was successful (#), will also be reported.

⁷⁴ IF tac_detect_zone = VF AND
(tac_assessment = sustained VT / VF OR
tac_assessment = non-sustained VT / VF) AND
tac_vf_atp_prog = 8 pulses with RS1 88% AND
tac_vf_first_therapy = ATP one-shot
THEN relevant_secEP_Ilivia_SAR = Yes
ELSE relevant_secEP_Ilivia_SAR = No

⁷⁵ IF any relevant_secEP_Ilivia_SAR = Yes per patient_display_id_full
THEN Ilivia_secEP_analysis_set_SAR = Yes
ELSE Ilivia_secEP_analysis_set_SAR = No

⁷⁶ IF Ilivia_secEP_analysis_set_SAR = Yes AND
any tac_vf_atp_success = Yes (regarding the relevant episodes) per patient_display_id_full
THEN Ilivia_secEP_SAR = Yes
ELSE Ilivia_secEP_SAR = No

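### Unless converted Early ATP one-shot episodes are coded as VF, eligibility for the ATP conversion endpoint depends on the outcome, and the rate could be understated

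*Protocol*

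**What the plan says.** Protocol 8.3.2.1.1 sets three conditions for an episode to count. The first is that "the arrhythmia was detected in the VF detection zone". The second is that the investigator confirms a true ventricular tachyarrhythmia. The third applies "if ATP one-shot was delivered with the recommended programming (8 pulses with 88% R-S1"). The patient-level success rule repeats the zone requirement: a patient is a success if "at least one episode detected in the VF zone in that patient was converted by ATP one-shot therapies" at that programming.

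SAP 17.2, footnote 74, begins "IF tac_detect_zone = VF AND" and adds the investigator's assessment, the programming, and ATP one-shot as first therapy. The zone item has four options: nsVT/nsT, SVT, VT1/VT2 and VF. First therapy is either ATP one-shot or shock.

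Protocol 4.7.5 describes Early ATP one-shot as "delivery of ATP prior to fulfilment of the programmed detection counter in the VF zone", triggered by a separate counter of 12 out of 16. During delivery "the VF counter is frozen and it continues to count after the ATP delivery for the initial detection". It also says: "If the early delivery of ATP one shot is successful, the VF counter will not be fulfilled and no shock therapy will be delivered". The feature is available only with a VF counter of at least 16 out of 20. For group A, Protocol 8.5.5 states that "programming of Early ATP one-shot is recommended and will be documented".

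**The concern.** On a literal reading, whether an Early ATP episode meets condition 1 depends on whether the ATP worked. A conversion stops the VF counter short, so the episode need not be a VF detection. After a failure the counter keeps running, and if it fills, the episode enters as a VF detection with ATP one-shot as first therapy and success recorded as No.

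Selecting on the outcome in this way would understate conversion. It would do so for the feature that Protocol 4.7.5 expects to raise ATP success, in an endpoint that Protocol 7.1.2.1.1 introduces to confirm that ATP one-shot is effective. It is group A's only secondary endpoint.

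**Working it through.** **Plan's own figure.** There is none to reproduce. The endpoint has no hypothesis, power or planned event count, only an exact two-sided 95% interval (SAP 17.6).

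**Step 1: follow each kind of episode through footnote 74.**

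| Episode | VF counter (Protocol 4.7.5) | Zone entry | In the analysis? |
|---|---|---|---|
| Regular ATP one-shot, either outcome | fulfilled before delivery | VF | Yes |
| Early ATP, converted | not fulfilled | not stated | Only if coded VF |
| Early ATP, not converted, counter then fills | fulfilled | VF | Yes, as a failure |
| Early ATP, not converted, rhythm leaves the zone or stops first | not fulfilled | not stated | Only if coded VF |

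**Step 2: look for text that settles the second row.** Footnote 74 also accepts an assessment of non-sustained VT/VF, but that is the investigator's rhythm call and zone = VF is still required. SAP 17.2 discusses ATP that is programmed but not delivered, and says nothing about Early ATP. Protocol 8.4.1 collects Early ATP programming and counts as further data of interest. Protocol 9.5 has sites evaluate VF and VT episodes as the device detected them. The SAP text has no Early ATP variable. The coding is left open.

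**Step 3: size in the worst case, per delivery.** Let p be true conversion (72% and 77% are the single-attempt rates cited in Protocol section 3) and e the share of deliveries that are Early ATP (assumed; the documents give none). Take one episode per patient, equal success for early and regular ATP, all Early ATP successes excluded and all failures kept:

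observed rate = p(1 − e) / [p(1 − e) + (1 − p)]

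| e | p = 72% | p = 77% |
|---|---|---|
| 25% | 0.54 / 0.82 = 66% | 0.5775 / 0.8075 = 72% |
| 50% | 0.36 / 0.64 = 56% | 0.385 / 0.615 = 63% |
| 75% | 0.18 / 0.46 = 39% | 0.1925 / 0.4225 = 46% |

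If converted Early ATP episodes are coded VF and failures are kept, the rate stays at p.

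**Step 4: how much rests on the failures.** If only a fraction k of Early ATP failures reach VF detection, the denominator becomes p(1 − e) + (1 − p)(1 − e) + k·e(1 − p). For p = 72% and e = 50%:

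- k = 1: 0.36 / 0.64 = 56%
- k = 0.5: 0.36 / (0.36 + 0.14 + 0.07) = 63%
- k = 0: 0.36 / 0.50 = 72%, no bias

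**Step 5: patient level.** The endpoint counts patients with at least one conversion. A patient with a counted regular success stays a success whatever else is lost. A patient whose only episodes are converted Early ATP leaves the denominator. A patient with an early conversion and a later counted failure is scored a failure.

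**Step 6: numbers expected.** Protocol 7.1.2.1.1 cites about 10% with appropriate therapy in 6 months: 0.10 × 94 = 9.4 and 0.10 × 105 = 10.5 patients, an upper bound because not all will have a VF-zone episode. Illustrative exact 95% intervals: 8/11 = 73% (39% to 94%) and 4/7 = 57% (18% to 90%).

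**The case against.** Protocol 8.3.2.1.1 speaks of detection in the VF zone, whereas Protocol 4.7.5 speaks of the VF counter. Early ATP is itself described as therapy belonging to the VF zone, the ATP items on the episode form carry a VF prefix, and a site that enters VF for a VF-rate arrhythmia treated this way would be within the text. The device label or the eCRF user guide may settle the matter, and neither is available here. This stands, and it makes the concern conditional: the problem is an eligibility rule that can depend on outcome, and whether it does so in practice is not shown.

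A reader might go further and infer that Early ATP successes are dropped, that every failure is kept, and that the reported rate will fall to 56% or 39%. The documents do not support this. They are silent on coding. They say only that the counter continues after Early ATP, so a failure need not reach VF detection. The figures are per delivery, with assumed shares, while the endpoint is per patient.

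Widening eligibility also has a cost. Some runs treated early might have ended unaided and would be credited to ATP, and both the objective and the cited benchmarks concern VF-zone detections. That stands, and it is a reason to show regular and Early ATP separately. It does not justify a filter that may act on one outcome more than the other.

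With about 10 patients the interval will be wide in any case. That limits the importance of the point, but a wide interval does not correct selection on the outcome.

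**Conclusion.** The point holds conditionally. As worded, condition 1 and footnote 74 let eligibility depend on outcome for a feature recommended in group A, and no other text prevents it. The direction would be downward, provided that converted Early ATP episodes are not all coded VF and that some failures reach VF detection. It would be nil if such episodes are coded VF whatever the outcome.

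At 72% true conversion, the loss at the extreme is about 6, 16 or 33 percentage points per delivery for assumed Early ATP shares of 25%, 50% or 75%. The patient-level effect would be smaller where a patient also has a counted success, and patients with VF counters below 16 out of 20 are outside it.

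The consequence is confined to a secondary endpoint with no hypothesis and no part in the pass/fail rule (Protocol 11.5). The primary endpoints and the sample size are unaffected.

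**What to change.** Make eligibility independent of outcome. Amend condition 1 of Protocol 8.3.2.1.1 and SAP footnote 74 to admit every episode confirmed as true ventricular tachyarrhythmia in which ATP one-shot, regular or Early, was delivered in the VF rate zone at 8 pulses and 88%, whatever the final episode label. Bring the patient-level success sentence and SAP 17.1 into line, and state that Early ATP is entered as ATP one-shot under first therapy. Add an Early ATP flag taken from the IEGM. Report conversion counts for regular and Early ATP one-shot separately, as description only, since Protocol 11.9 plans no further subgroup analysis.

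The cost is mainly wording and one derived flag. Protocol 8.5.7 already makes IEGMs mandatory for group A therapy and therapy-attempt episodes, and Protocol 8.4.1 already collects Early ATP counts. Two costs should be named in the text. Converted Early ATP episodes logged as nsVT may need an episode form completed from the stored IEGM. The Early ATP rate may also be slightly flattering, because some runs might have stopped unaided. If the device or the eCRF guide already codes these episodes as VF, one sentence in the SAP saying so would resolve the ambiguity.

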8.3.2.2 Secondary endpoints and hypotheses **Group B:** Plexa

8.3.2.2.1 Rate of appropriate right ventricular sensing at 3-month follow-up

This secondary hypothesis evaluates the rate of appropriate right ventricular sensing (Plexa_{Sensing}) of all patients in which sensing measurement was performed. It is expected, that the rate will be significantly above 93%, the corresponding hypotheses definitions are:

Null hypothesis: $H_{0_Sensing} : Plexa_{Sensing} \leq 93\%$

Alternative hypothesis: $H_{A_Sensing} : Plexa_{Sensing} > 93\%$

The investigator is asked to determine if the lead system is appropriately sensing the intrinsic ventricular signals at the end of each scheduled follow-up. The evaluation of ventricular sensing is based on the assessment of 10 consecutive intrinsic signals documented with markers on an IEGM (see 8.5.11). Only the evaluation of the 3-month follow-up is taken into account towards data analysis of this endpoint. Only patients with measurements performed at the 3-month follow-up will be included in this analysis set. Specifically, the percentage of patients with an appropriate RV sensing at the 3-month follow-up will be determined.

The parameter of interest Plexa_{Sensing} is the rate of patients with appropriate sensing which will be calculated by

Plexa_{Sensing} = (Number of patients with appropriate sensing (Sensing_{app}) divided by number of patients with sensing measurements performed) * 100%.

Patients, in whom the sensing performance cannot be evaluated or has not been evaluated, will not contribute to the analysis set ("no intrinsic rhythm" and "not done").

8.3.2.2.2 Rate of appropriate right ventricular pacing at 3-month follow-up

This secondary hypothesis evaluates the rate of appropriate right ventricular pacing (Plexa_{Pacing}) of all patients in which pacing measurement was performed. It is expected, that the rate will be significantly above 93%, the corresponding hypotheses definitions are:

Null hypothesis: $H_{0_Pacing} : \text{Plexa}_{Pacing} \leq 93\%$

Alternative hypothesis: $H_{A_Pacing} : \text{Plexa}_{Pacing} > 93\%$

The investigator is asked to determine if the pacing system is appropriately pacing the ventricle at the end of each scheduled follow-up. The evaluation of ventricular pacing is based on the assessment of 10 consecutive beats documented with markers on an IEGM (see 8.5.11). Only the evaluation of the 3-month follow-up is taken into account towards data analysis of this endpoint. Only patients with measurements performed at the 3-month follow-up will be included in the endpoint.

Specifically, the percentage of patients with an appropriate RV pacing at the 3-month visit will be determined.

The parameter of interest Plexa_{Pacing} is the rate of patients with appropriate pacing which will be calculated by

$\text{Plexa}_{Pacing} = (\text{Number of patients with appropriate pacing (Pacing}_{app}) \text{ divided by number of patients with pacing measurements performed}) * 100\%$.

According to the definitions provided in section 8.5.11, the pacing performance can be "adequate" or "inadequate". If reason for inadequate performance is "No capture", the evaluation will not be considered an endpoint-related event in case the underlying reason is a medical event (e.g. hyperkalaemia, myocardial infarction or drug therapy). Patients, in whom the pacing performance has not been evaluated, will not contribute to the analysis set ("not done").

8.4 Further data of interest

Besides endpoint-relevant data, the following further data will be collected and assessed:

8.4.1 Further data of interest in group A (Ilivia ICD family)

- MPP settings

The MPP settings used by the physicians will be collected for all CRT-D patients programmed to MPP "on". This includes the programmed vectors, the pacing threshold, the programmed pacing amplitudes, the LV sensing polarity, the sensing amplitude, the LV-LV and RV-LV delay as well as any change of setting during the course of the study.

- Handling of MPP programming (interface programmer)

The physician is asked to evaluate the handling of the MPP programming in an eCRF "MPP handling".

- SADE related to MPP during 6 months

SADEs which are possibly or securely related to MPP will be listed in a descriptive manner.

- Rate of responders/ non-responders to CRT therapy

These data will be collected from all patients implanted with a CRT-D device of the Ilivia family. The physician should evaluate at the 6-month follow-up if the respective patient is a responder or a non-responder to CRT-D therapy. Patients who did not tolerate MPP and had to be reprogrammed to MPP "off" during the course of the study contribute to the MPP "off" group.

- NYHA class, change of NYHA class in CRT-Ds

The NYHA class will be collected at baseline from all patients and at 6-month follow-up for CRT-D patients only. The mean change of NYHA class in CRT-D patients between enrollment and 6-month follow-up will be evaluated.

- Percentage of DX devices among devices, DX in CRT, atrial sensing amplitude in DX devices

Data of DX devices will be collected, including the percentage of used DX devices in ICD and CRT-D therapy. Furthermore the atrial sensing amplitude of DX devices as well as CRT statistics will be collected and the mean values evaluated at 3- and 6-month follow-up.

- Ventricular therapy episodes

Ventricular therapy and therapy attempt episodes will be collected and documented in a tachyarrhythmia episode eCRF, IEGMs of the episodes will be collected.

- Programming of Early ATP one-shot

The number of programming of Early ATP one-shot will be documented for all patients with programming of ATP one-shot in the VF zone. Number of occurred Early ATP one-shot will be collected based on the documented ventricular tachycardia IEGM episodes.

- Lead measurements (sensing amplitude, pacing threshold, pacing impedance, shock impedance) via pacing sensing analyzer (PSA) during implantation

Lead measurements via PSA will be performed prior to connection of the leads to the ICD device. Mean values from all patients will be calculated for each type of lead for each type of measurement.

- Lead measurements (sensing amplitude, pacing threshold, pacing impedance, shock impedance)

Lead measurements will be performed during each follow-up for all available leads. Mean values from all patients will be calculated for each type of lead and for each type of measurement.

- Evaluation of sensing and pacing performance

The sensing and pacing performance of the device will be evaluated by the physician in all available channels. Mean values will be determined for each type of lead.

- IEGMs of non-sustained VTs, fast intervals and atrial episodes

All IEGMs of non-sustained VTs, fast intervals and atrial episodes will be collected for possible further evaluation. In addition the last 3 occurred episodes prior to the respective follow-up will be evaluated and entered in the tachyarrhythmia episode form

- Home Monitoring data

Pseudonymized Home Monitoring data will be collected throughout study duration for potential further evaluations of continuously available device data.

- Adverse Events / Device Deficiencies

All AEs and DDs will be collected during the course of the study in a descriptive manner.

- MRI AutoDetect functionality

Information on MRI AutoDetect functionality will be collected for patients undergoing MRI during the course of the study. This includes available Home Monitoring Data and further information provided by the cardiologist (if available).

